13.5.3 Laboratory analysis

Laboratory data that are continuous in nature but are less than the lower limit of quantitation or above the upper limit of quantitation will be imputed. The limit of quantitation will be used for calculation of descriptive statistics if the data is reported in the form of " $\leq x$ " or " $< x$ " or " $\geq x$ " (x is considered as the limit of quantitation).

The following analysis on laboratory parameters will be performed:

- i. Laboratory parameters will be summarized. Descriptive summaries of actual (absolute) values and change-from-baseline values will be presented for haematology and serum chemistry for the SAF by visit. SI units will be used in the generation of these descriptive summaries. The assessment of categorical urinalysis variables will be tabulated by time point for each categorical urine parameter.
- ii. Abnormal values will be flagged in the listings (SAF population) to indicate whether the value is below or above the reference range and whether the investigator assessed the abnormal value as clinically significant. A clinically significant result can be commented with "Adverse Event", "Due to primary disease", "Pre-existing condition" or free text.
- iii. The assessment of the clinical significance of laboratory variables will be tabulated by time point for each clinical laboratory analyte.
- iv. For each laboratory parameter, shifts in assessments from baseline to worst-post baseline will be presented.
- v. If NCI-CTCAE grades are available for a clinical laboratory analyte, they will be derived according to NCI CTCAE, Version 4.03, and used to present additional frequency and shift tables based on NCI-CTCAE grades.

The following summary will be produced for the laboratory data (by laboratory parameter):

-
- Number (%) of patients with worst post-baseline CTCAE grade (regardless of the baseline status). Each patient will be counted only for the worst grade observed on-treatment
 - Shift tables to compare baseline to the worst post-baseline value will be produced for hematology and biochemistry laboratory parameters using:
 - CTCAE grades for laboratory parameters where CTCAE grades are defined.
 - The classifications relative to the laboratory reference ranges (low/normal/high) for laboratory parameters where CTCAE grades are not defined.
- vi. The following listing will be produced:
- Listing of patients with laboratory values outside the normal ranges with values flagged to show the corresponding CTCAE grade and the classifications relative to the laboratory reference ranges.

The summaries will include only assessments on treatment. The analysis will be performed on the SAF.

13.6 ECOG scores analyses

The analysis of ECOG scores will be performed on FAS and SAF.

The following analyses will be performed on ECOG scores:

- The ECOG performance status will be summarized categorically in a frequency table by visit.
- Shift Tables in ECOG status from baseline to worst post-baseline will be presented.
- The ECOG status will be listed (for the SAF).

13.7 B-symptoms

B-symptoms are defined as any one or more of the following disease-related symptoms or signs:

- Unintentional weight loss of $\geq 10\%$ within the preceding 6 months or less.
- Drenching night sweats without signs of infection.
- Recurrent, unexplained fever with temperatures above 38 °C without signs of infection.

The presence of B-symptoms will be summarized categorically in a frequency table by visit. The analysis will be performed on FAS and SAF. Data listings will be presented (for the SAF).

14. GENERAL GUIDANCE ON REPORTING

14.1 Document headers and footers

The following header will be used for all tables, listings and figures outlined in this document: MOR208C203 – *reporting event* (Cut-off date ddMONyyyy).

The following labels of *reporting event* will be used for all outputs:

- PA for Primary Analysis
- FA for Final Analysis

The following display will be used for outputs:

- footnote 1
- footnote 2
- footnote 3

program source, date and version information.

For example:

```
MOR208C203- PA (Cut-off date: 06JUN2014)
"/report/pgm_saf/program.sas 07MAY14:15"
```

In the applicable outputs, the MedDRA version and WHO-DDE version used for reporting the study will be specified as a footnote.

- MedDRA Version <xx.x> has been used for the reporting
- WHO-DDE Version <xx.x> has been used for the reporting

The latest available version of dictionaries at the time of reporting will be used.

14.2 Presentation of output numbering and titles within this document

In practice, the numbering and title for all tables, figures and listings in sections 14 and 16 defined in this document will be formatted as follows, respectively:

Table XX.X-X.X
Title Title Title Title Title Title
Population

Listing XX.X-X.X

Title Title Title Title Title Title

Population

14.3 Presentation of analysis sets

The outputs to be produced based on this document will use ‘Screened Patients’, ‘Enrolled Patients’, ‘FAS’, ‘PPS’, ‘SAF’, ‘PKAS’, ‘IAS’ in the table/figure/listing titles.

14.4 General rules for presenting frequencies and percentages

If a summary table displays only categorical variables then the convention illustrated in the following example will be used:

Preferred Term	N=xx n (%)
Total	xx (xx.x)
Fatigue	xx (xx.x)
Nausea	xx (xx.x)
Anemia	xx (xx.x)

However, if a summary table displays both continuous and categorical variables then the convention illustrated in the following example will be used:

STATISTICAL ANALYSIS PLAN

 MorphoSys AG
 MOR208C203

	All patients
	N=xx
Sex, n (%)	
Male	xx (xx.x)
Female	xx (xx.x)
Age (Years)	
n	xx
Mean	xx.x
StD	xx.xx
Median	xx.x
Minimum	xx.x
Maximum	xx.x

14.5 General rule for tables/listings

All other data as documented in the eCRF will be listed and/or tabulated using descriptive statistics or counts/percentages depending on the nature of data. All the data collected and derived in the trial will be presented in patient data listings.

14.6 Format of tables/listings and displays with no data

Where a listing or table has been planned, but no data meet the criteria, then a single line stating 'No data meeting the criteria are present' will be provided in the output. The default tables, listings and figures (TLF) layout will be as follows.

Orientation	Landscape
Paper Size	A4
Margins	Top: 2 cm Bottom: 2 cm Left: 2 cm Right: 2 cm Header: 1.27 cm Footer: 1.27cm
Font	Courier New 8pt
Headers	Protocol number – Type of Analysis (Cut-off date) (Left); Page X of Y (Right) TLF Number and Title
Footers	SAS program name Source Data File name Extract date Date, Time TLF generated

The font size may be reduced as necessary to allow additional columns to be presented, but not at the expense of clarity. Also the orientation may be changed to portrait if appropriate.

14.7 Precision rules

For continuous variables, minimum and maximum will be presented to the same precision as the raw data. Mean, median, 25th and 75th percentiles will be presented to one more decimal place and standard deviation to two more decimal places than the raw data. An exception will be made for biomarker representing counts where mean and median will be presented without a decimal place. Geometric mean will be presented to one more decimal place than the raw data. CV of mean and CV of geometric mean will be shown to one decimal place.

For concentrations and PK parameters 3 significant digits apply for mean, geometric mean, median, StD, min and max. Elapsed time and Tmax should have 2 decimal places in the listings.

For categorical variables, the number (n) and percentage (%) of patients per category will be presented. If the count is zero in a cell, then only '0' count will be presented and not '0.0 (0.0)'. The number of missing values will be presented as a "Missing" category. Percentage

values are to be rounded and presented to one decimal place. If percentages are equal to 100, then no decimal places will be presented 'xx (100)'.

The confidence intervals of a percentage will be presented to the same precision as the percentage. The p-values will be presented with three decimals. P-values below 0.001 will be denoted as <0.001. Hazard ratios and respective confidence intervals will be presented to two decimal places.

14.8 General rules for presenting listings

The following general rules for presenting listings should be applied by default for all listings.

For listings, the default sorting order is by patient number and event/assessment date unless otherwise stated.

The first column of the listing will always be "Patient identifier" field.

Where a listing or table has been planned, but no data meet the criteria, then a single line stating 'No data meeting the criteria are present' will be provided in the output.

The study day will always be displayed in the listings if applicable. It will be printed under the label 'Study Day' in all listings. The definition of study day is:

The reference start date **for all safety assessments** (e.g. adverse event onset, laboratory abnormality occurrence, vital sign measurement, dose interruption, etc.) will be the start date of study treatment. The following footnote will be added in all safety listings: "Study Day is relative to the first date of study treatment (Day 1)".

The reference start date **for all efficacy assessments** (e.g. tumor assessment, death, disease progression, tumor response, performance status) will be the start date of study treatment. The following footnote will be added in all efficacy listings: "Study Day is relative to the first date of study treatment (Day 1)".

For data collected at the visit level: 'Visit' column will be displayed in the listings. Unscheduled visits will appear as "Unsch" (or similar) in all the listings, if any.

For all laboratory parameters, SI units are used as default.

When a variable collected in the eCRF is linked to another variable, one or both variables will be presented in the same column of the listing or in adjacent columns if space permits this.

For example:

- 'Setting'='OTHER' and 'Other, specify'='Lung'
'OTHER: Lung' will be displayed in the column as 'Setting'.
- 'Dose'='120' and Dose unit ='mg'
'120 mg' will be displayed in the column as 'dose (unit)'.

-
- Date = "2012-05-12" and Study day ="5".
 - "12MAY2012 / 5" will be displayed in the column as 'Date / Study Day'.
 - (1) End date = "2012-05-22" and Study day ="15" or
(2) End date = " " and ongoing is ticked:
 - (1) "22MAY2012 / 15" will be displayed in the column as 'End date / Study Day'
 - (2) "Ongoing" will be displayed in the column as 'End date / Study Day'.

14.9 Presentation of Dates

Calendar dates and times (optional) in all the listings will be displayed in the format:

DDMMYYYY/hh:mm e.g. 2011-01-15/00:20.

Note: If time is not collected, calendar dates will be displayed as: DDMMYYYY.

16. ADDENDUM 1.0

16.1 Compliance

The compliance for MOR00208 and LEN as outlined in Section 8.9.6 is summarized by Cycle. Boxplots showing the distribution of compliance within the patient population will be produced. The analyses will be performed for both the FAS.

16.2 Relative dose intensity

The dose intensity of LEN and MOR00208 as defined below will be summarized by Cycle. Boxplots will be generated showing the distribution of the relative dose intensity. The analyses will be conducted using the FAS.

The relative dose intensity for LEN is derived as follows:

- „Planned dose“ for each Cycle: 25 mg x 21 days = 525 mg per Cycle (ignoring dose change, interruptions, discontinuations)
- „Used dose“ for each Cycle: X mg total daily dose x number of pills taken in that Cycle (pills returned – pills dispensed will be used as surrogate for pills taken)
- Relative Dose Intensity by Cycle: „Used dose“ / „Planned dose“ x 100
- A boxplot showing the distribution of the Relative Dose Intensity by Cycle will be generated

The relative dose intensity for MOR00208 is derived as follows:

- „Planned dose“ for a particular Cycle: 250 ml x planned number of infusions for a particular Cycle (varies depending on the Cycle)
- Infusion interruptions and skipped doses will be ignored when determining the „planned dose“
- „Used dose“ for a particular Cycle: sum of actual volume administered across all infusions of a Cycle
- Relative Dose Intensity by Cycle: „Used dose“ / „planned dose“ x 100
- A boxplot showing the distribution of the Relative Dose Intensity by Cycle will be generated

16.3 Additional safety analyses

For all additional safety analyses specified in the SAP Addendum the general approach for reporting the incidence and frequency of adverse events is used as detailed in Section 10.7.

16.3.1 TEAE by 'search category'

The incidence of TEAEs will be summarized by 'search category', PT, and NCI-CTCAE Grade. The following search categories are defined:

1) Search Category: 'Infective pneumonias'

All AEs belonging to Standardised MedDRA Query (SMQ) "Infective pneumonias" will be displayed in a combined fashion. For instance, the following terms will be pooled:

- PT pneumonia
- PT lung infection

2) Search Category: Sepsis

All AEs with PTs including the term "Sepsis" (in MedDRA: 54 terms) will be displayed in a combined fashion. For instance, the following terms will be pooled:

- PT sepsis
- PT neutropenic sepsis
- PT streptococcal sepsis
- PT Klebsiella sepsis

3) Search Category: Urinary tract infections

All AEs with PTs including the term "Urinary tract infection" (in MedDRA: 42 terms) plus all AEs belonging to MedDRA HLT "Urinary tract infections" will be displayed in a combined fashion, for instance, the following terms will be pooled:

- PT urinary tract infection
- PT urinary tract infection bacterial
- PT Escherichia urinary tract infection
- PT urinary tract infection enterococcal

4) Search Category: Rashes

All AEs belonging to MedDRA HLGT "Epidermal and dermal conditions" will be displayed in a combined fashion, for instance, the following terms will be pooled:

- PT rash

-
- PT rash maculo-papular
 - PT rash erythematous
 - PT rash pruritic
 - PT dermatitis allergic

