16.3.2 Time to first TEAE

The time to the first TEAE will be summarized for the following TEAEs:

- Neutropenia \geq G3 (PT 'neutropenia')
- Thrombocytopenia \geq G3 (PT 'thrombocytopenia')
- Infections and infestations \geq G3 (SOC 'infections and infestations')
 - Infective pneumonia \geq G3 (SMQ code 20000231, narrow scope)
- Urinary tract infection \geq G3 (CMQ as defined in the SAP Appendix)
- Sepsis \geq G3 (CMQ as defined in the SAP Appendix)
- Febrile neutropenia (PT 'febrile neutropenia')
- Thromboembolic events of all CTCAE Grades (SMQ code 20000081)
- Thromboembolic events \geq G3 (SMQ code 20000081)

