16.5.2 Patients who reduced the daily prescribed LEN dose

Incidence and frequency of TEAEs by the degree of LEN dose reduction

TEAEs will be tabulated by SOC, PT, and NCI-CTCAE Grade as described in Section 10.7 for the following subgroups of patients:

- Patients with no reduction of LEN.
- Patients with a minimum LEN dose of 20 mg/day: for this category, all TEAEs that occurred *before* exceeding the threshold of 20 mg/day are considered. The calculation of incidence rates is based on the number of patients in the SAF.
- Patients with a minimum LEN dose of <20 mg/day but ≥5mg/day: for this category, all TEAEs are considered that happened *after* exceeding the threshold of 20 mg/day. The calculation of incidence rates is based on the number of patients who had a reduction to <20 mg/day but ≥5mg/day.

Duration of TEAEs of interest

The duration of various TEAEs of interest will be summarized for the following dose categories:

- Patients who are treated with 25 mg LEN per day
- Patients who are treated with 20 or 15 or 10 or 5 mg LEN per day
- Patients who are treated with 15 or 10 or 5 mg LEN per day

For each category only those TEAEs are considered that happen *during* the period of treatment with the particular dose or dose range defining the categories above (e.g., only those TEAEs are considered that happen during while the patient is on 15 or 10 or 5 mg LEN per day). The duration of a particular TEAE is summarized for the following TEAEs:

- Neutropenia ≥G3 (PT 'neutropenia')
- Thrombocytopenia ≥G3 (PT 'thrombocytopenia')
- Infections and infestations ≥G3 (SOC 'infections and infestations')
- Infective pneumonia ≥G3 (SMQ code 20000231, narrow scope)
- Urinary tract infection ≥G3 (CMQ as defined in the SAP Appendix)

-
- Sepsis \geq G3 (CMQ as defined in the SAP Appendix)
 - Febrile neutropenia (PT 'febrile neutropenia')
 - Thromboembolic events of all CTCAE Grades (SMQ code 20000081)
 - Thromboembolic events \geq G3 (SMQ code 20000081)

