APPENDIX: LIST OF CUSTOMIZED MEDDRA QUERIES

Sepsis (CMQ)	PT	PTCD
	Escherichia sepsis	10015296
	Meningococcal sepsis	10027280
	Postpartum sepsis	10036422
	Sepsis	10040047
	Sepsis neonatal	10040049
	Sepsis pasteurella	10040051
	Umbilical sepsis	10045470
	Urosepsis	10048709
	Streptococcal sepsis	10048960
	Neutropenic sepsis	10049151
	Pulmonary sepsis	10051739
	Candida sepsis	10053166
	Group B streptococcus neonatal sepsis	10053588
	Bacterial sepsis	10053840
	Sepsis syndrome	10053879
	Pneumococcal sepsis	10054047
	Stenotrophomonas sepsis	10054137
	Klebsiella sepsis	10054160
	Micrococcal sepsis	10054162
	Brucella sepsis	10054210
	Citrobacter sepsis	10054213
	Enterobacter sepsis	10054219
	Enterococcal sepsis	10054221
	Helicobacter sepsis	10054264

STATISTICAL ANALYSIS PLAN

 MorphoSys AG
 MOR208C203

	Staphylococcal sepsis	10056430
	Corynebacterium sepsis	10057767
	Biliary sepsis	10057847
	Abdominal sepsis	10058040
	Wound sepsis	10058041
	Fungal sepsis	10058872
	Anthrax sepsis	10058873
	Haemophilus sepsis	10058875
	Herpes sepsis	10058876
	Pseudomonal sepsis	10058877
	Salmonella sepsis	10058878
	Serratia sepsis	10058879
	Plague sepsis	10058889
	Pseudallescheria sepsis	10058973
	Pelvic sepsis	10059070
	Listeria sepsis	10063085
	Nocardia sepsis	10064952
	Pseudosepsis	10064991
	Post procedural sepsis	10066593
	Burkholderia cepacia complex sepsis	10069684
	Device related sepsis	10069802
	Campylobacter sepsis	10070681
	Viral sepsis	10071362
	Yersinia sepsis	10072902
	Herpes simplex sepsis	10074246
	Shigella sepsis	10074481
	Intestinal sepsis	10075622
	Clostridial sepsis	10078496

STATISTICAL ANALYSIS PLAN

 MorphoSys AG
 MOR208C203

	Erysipelothrix sepsis	10080432
	Actinomycotic sepsis	10080434

Urinary Tract Infections (CMQ)	PT	PTCD
	Urinary tract infection	10046571
	Urinary tract infection enterococcal	10046572
	Urinary tract infection neonatal	10046573
	Urinary tract infection fungal	10049059
	Cytomegalovirus urinary tract infection	10051350
	Escherichia urinary tract infection	10052238
	Urinary tract infection bacterial	10054088
	Genitourinary tract infection	10061182
	Urinary tract infection pseudomonal	10062279
	Urinary tract infection staphylococcal	10062280
	Urinary tract infection viral	10064825
	Prophylaxis urinary tract infection	10066700
	Streptococcal urinary tract infection	10070300
	HLT	HLTCD
	Urinary tract infections	10046577

STATISTICAL ANALYSIS PLAN

 MorphoSys AG
 MOR208C203

Opportunistic infections (CMQ)	PT	PTCD

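### The text-matched sepsis query leaves out septic-shock terms and counts Pseudosepsis, so events are misclassified in the pooled sepsis, onset and duration outputs, though not lost from the safety analysis

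*SAP*

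**What the plan says.** SAP 16.3.1 defines four pooled adverse event categories. Infective pneumonias use a standardised MedDRA query, rashes use a high-level group term, and urinary tract infections use a text match plus a high-level term. Sepsis alone rests on a text match only: preferred terms (PTs) containing the word 'Sepsis', of which it says "in MedDRA: 54 terms) will be displayed in a combined fashion". The Appendix prints the list. It includes "Neutropenic sepsis" and many organism-specific terms, and also "Pseudosepsis". The urinary list beside it includes "Prophylaxis urinary tract infection".

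The lists are used well beyond the incidence table:

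- 16.3.2: "The time to the first TEAE will be summarized for the following TEAEs". For sepsis and urinary tract infection the definition is "G3 (CMQ as defined in the SAP Appendix".
- 16.5.1 tabulates the 16.3.1 search categories before and after lenalidomide discontinuation.
- 16.5.2, by lenalidomide dose: "The duration of a particular TEAE is summarized for the following TEAEs", with the same Appendix queries.
- 20.13 uses the sepsis and urinary queries, at all grades and at grade 3 or above, for time to onset, duration and cumulative duration per exposure.

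In 16.3.2, 16.5.2 and 20.13, neutropenia and thrombocytopenia are each defined by a single PT (for example "PT 'neutropenia").

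**The concern.** A pooled category exists to give one patient-level count for one medical concept. A rule based on spelling gives that only if every relevant term shares the spelling and no irrelevant term does. Here neither holds. Septic shock is part of the sepsis concept but is spelled differently, while Pseudosepsis and urinary infection prophylaxis share the spelling but, by their names, not the concept.

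What is at stake is the sepsis rate that a reader would take from the grouped table, the comparison before and after lenalidomide discontinuation, and the statements on when sepsis starts and how long it lasts. Safety of the combination is secondary objective 7. With about 80 patients, one or two misplaced events are visible in a small category.

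**Working it through.** **Reproducing the plan's figure.** Counting the Appendix Sepsis list gives 54 distinct PTs, which agrees with the 54 stated in 16.3.1. The Appendix therefore applies the rule faithfully, and the fault lies in the rule.

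**Testing the list** (ignoring case):

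| Test | Result |
|---|---|
| PTs containing 'sepsis' | 54 of 54 |
| PTs containing 'septic' or 'shock' | 0 of 54 |
| Does the text 'septic shock' contain 'sepsis'? | No |
| Pseudosepsis on the list | Yes (53 terms remain without it) |
| 'Sepsis' present only as part of a longer word | 2: Urosepsis and Pseudosepsis |

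The third row settles the main point: no event coded to a term worded as septic shock can meet the rule, whatever its grade.

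**The urinary list.** The Appendix prints 13 PTs plus one high-level term. One of the 13 is the prophylaxis entry, so 12 remain without it. Section 16.3.1 states 42 terms for the text match. The printed list does not reproduce that figure and the documents do not explain the difference, so it should be reconciled in the same edit.

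**Which outputs are affected.**

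| Output | Uses the sepsis list | Unrestricted equivalent for sepsis |
|---|---|---|
| Pooled incidence, 16.3.1 | Yes | None: PT rows cannot be summed to patients, because one patient may be in several rows |
| Before/after lenalidomide, 16.5.1 | Yes, by search category | All events are also shown by PT, but not pooled |
| Time to first event, 16.3.2 | Yes, grade 3 or above | Only the whole infections class, which is too broad |
| Duration by lenalidomide dose, 16.5.2 | Yes, grade 3 or above | Same |
| Onset, duration and cumulative duration, 20.13 | Yes, all grades and grade 3 or above | Same |

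**Size.** The documents give no event counts. Taking about 80 treated patients, the planned enrolment, a patient whose only sepsis-type event is coded to a septic-shock term lowers the pooled incidence by 1/80 = 1.25 percentage points. A patient whose only entry is Pseudosepsis raises it by the same amount. A patient who also has an event under a listed sepsis PT stays in the count; at most the onset or duration changes. The net direction is therefore not known in advance.

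**The case against.** The strongest reply is that nothing disappears. SAP 10.7.3 tabulates all treatment-emergent events, those of grade 3 or above, and grade 3/4 events by class, PT and grade without restricting terms. It does the same for serious events and lists grade 5 serious events by class and PT. Section 16.5.1 shows all, serious, grade 3 versus 4 and fatal events around lenalidomide discontinuation. Section 20.12 shows events leading to interruption or reduction. All of this stands, and it limits the point to grouped, onset and duration outputs.

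A reader might infer more: that key severe toxicities are undercounted, or that the sepsis rate leaves out its life-threatening and fatal cases. The documents do not support either reading. A grade 4 or 5 event coded to any of the 54 listed PTs is counted, and 16.3.1 tabulates by grade. The two false entries raise counts rather than lower them.

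A reader might also infer that the single-PT definitions make the neutropenia and thrombocytopenia results incomplete. That is not shown. These definitions are not 16.3.1 search categories and affect only the onset and duration summaries. Protocol 8.2 steers sites towards recording diagnoses. Laboratory values, including neutrophils and platelets, are graded independently of event wording (SAP 13.5.3). The documents name no alternative PT for a low count. Still, the protocol's definition of an adverse event includes abnormal laboratory findings, so differently worded entries cannot be excluded. Section 20.13 itself pools PTs for other concepts, such as fatigue with asthenia. A check is warranted; a finding of undercounting is not.

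**Conclusion.** The point holds as a misclassification in supplementary safety outputs. The sepsis query excludes septic-shock terms by construction and admits Pseudosepsis, and the urinary query admits a prophylaxis term. It affects the pooled incidence in 16.3.1 and 16.5.1 and the onset and duration summaries in 16.3.2, 16.5.2 and 20.13. It does not affect the primary endpoint or the main adverse event tables.

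The size cannot be determined from the documents; it is 1.25 percentage points of pooled incidence per patient misplaced, with errors possible both ways. The conclusion rests on two assumptions: that the MedDRA version used has PTs for septic shock worded without 'sepsis', which the documents do not list, and that at least one event is coded to such a term or to a false entry. If no such event occurs, the outputs will not change, but the definition would still be wrong as written.

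**What to change.** - In 16.3.1 and the Appendix, replace the text match with a sepsis query defined by medical concept, including the septic-shock terms of the MedDRA version used.
- Remove Pseudosepsis from the sepsis query and the prophylaxis term from the urinary query. Change the rule text in 16.3.1 as well as the lists, because the text match would otherwise bring both entries back, and confirm that the urinary high-level term does not reintroduce the second. Reconcile the stated 42 urinary terms with the printed list.
- Before database lock, have drug safety check the lists against every PT coded in the study. Include whether any low neutrophil or platelet event was coded to a PT other than 'neutropenia' or 'thrombocytopenia'. If so, add those PTs to the definitions in 16.3.2, 16.5.2 and 20.13; if not, leave them unchanged.

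The cost is a few lines in the Appendix, one review of coded terms and rerun tables. There is no change to design or data collection. The downside is that the reported rates may become slightly less favourable.
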